2.0 TRIAL DESIGN

2.1 Trial Design

This is an open-label, single-dose study to evaluate the pharmacokinetics (PK) of intravenous (IV) MK-3866 in subjects with moderate and severe hepatic impairment (HI) compared to that of matched healthy subjects. Subjects with moderate (Panel A) and severe (Panel B) HI (classified using the Child-Pugh scale) shall be enrolled in parallel, and each Panel shall enroll a minimum of 2 subjects of each gender.

Enrollment of healthy matching control subjects (Panel C) shall commence following the completion of enrollment of either Panel A or B, whichever is completed first. Each healthy control subject will be matched to the mean body mass index (BMI; $\pm 10\%$) and age (± 15 years) of the subjects in the first HI Panel to complete enrollment. A total of 6 healthy subjects shall be enrolled into Panel C at this stage, and there should be a minimum of 2 subjects of each gender.

Following the completion of enrollment of the second HI panel, the matching characteristics (age and BMI) of the already-enrolled healthy subjects in Panel C will be compared against the mean values of the HI panel that is completed second. If any of the subjects already enrolled in Panel C do not also meet the matching criteria for the second completed HI panel, additional healthy subjects will be enrolled into Panel C in order to provide 6 healthy control

subjects who match the mean BMI ($\pm 10\%$) and age (± 15 years) of the subjects in the second HI panel. The gender of the additional healthy subject(s) will be selected to ensure that there is a minimum of 2 subjects of each gender in the group of subjects within Panel C who match with the second HI panel. On the basis of this study design Panel C may ultimately include more than 6 subjects, but no more than 12. Although enrollment efforts into Panels A and B will commence at the same time, it is expected to take longer to enroll subjects into Panel B.

The PK comparisons between each hepatically impaired Panel (A and B) and healthy controls (Panel C) will include only control subjects who meet the matching criteria for the respective HI panel.

Subjects in Panels A, B and C will receive a single IV dose of 150 mg MK-3866 (30 minute infusion, ± 5 minutes). Plasma PK assessments will be performed at pre-specified time points up to 72 hours post-dose for moderate and severe HI and up to 48 hours postdose for the healthy match control group.

[figure not shown]

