8.0 STATISTICAL ANALYSIS PLAN

8.1 Statistical Analysis Plan Summary

8.1.1 Source of Variance Estimates: Precision and Sample Size

The sample size selected for each population to evaluate the effect of HI on the PK of MK-3866 was not chosen to satisfy any a priori statistical requirement. This sample size (N=6 per group) has historically been shown to be sufficient for studies of this type and should provide adequate data to support the planned analyses. Nevertheless, estimates of the expected precision of the estimates based on these sample sizes are presented below.

The precision of the estimates of ratios of geometric means obtained from this study can be assessed by calculating the half-width of the 90% confidence intervals expected for the given sample size and assumed variability. The estimated between-subject variance for log AUC_{0-∞} is 0.0196 log ng•hr/mL from a previous study (PN001). Since the between subject variability in severe hepatic insufficient subjects is usually higher in many studies, the between subject variability obtained from healthy were inflated by a factor of 2 for severe hepatic insufficient subjects and was used for the following calculations. With 6 hepatic insufficient subjects and 6 healthy matched subjects, the half-width of the 90% confidence interval for the arithmetic mean AUC_{0-∞} on the log scale will be 0.179 log ng•hr/mL. The lower and upper 90% confidence limits for the true ratio of geometric means will be given by OBS/1.163 and OBS x 1.197, where OBS is the observed ratio of geometric means. Thus, for example, if the observed ratio of geometric means was 1.5, the 90% confidence interval would be (1.25, 1.79).

8.1.2 Statistical Core Methods:

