8.1.2.1 Primary PK Analysis

Separately for each pharmacokinetic parameter, individual values of AUC_{0-∞}, AUC_{0-last}, AUC₀₋₂₄, C_{eo}, and CL will be natural log-transformed and evaluated with a linear fixed effects model containing a categorical effect for populations. The REPEATED statement with the GROUP=Population option will be used in SAS PROC MIXED to estimate separate variances for each population. The Kenward and Roger adjustment will be used to calculate the denominator degrees of freedom for the fixed-effect (DDFM=KR). Ninety-five percent (95%) confidence intervals for the least squares means for each population will be constructed on the natural log scale and will reference the t-distribution. Exponentiating the least-squares means and their corresponding 95% confidence intervals will yield estimates for the population geometric means and confidence intervals about the geometric means on the original scale.

To compare subjects with HI in each of the hepatic insufficient categories (moderate HI and severe HI) to matching subjects with normal hepatic function, a two sided 90% confidence interval for the true difference in means (HI – normal hepatic function) will be calculated for each PK parameters (AUC_{0-∞}, AUC_{0-last}, AUC₀₋₂₄, C_{ei}, and CL) using the mean square error from the model and referencing a t-distribution. For each of the HI populations, these confidence limits will be exponentiated to obtain the 90% confidence interval for the true ratio of geometric means (HI/normal hepatic function) for each pharmacokinetic parameter.

Figures showing individual pharmacokinetic values with GMs (95% confidence intervals) by population, plotted on the natural log scale, will be provided for AUC_{0-∞}, AUC_{0-last}, AUC₀₋₂₄, C_{ei}, and CL.

Individual values will be listed for each PK parameter (AUC_{0-∞}, AUC_{0-last}, AUC₀₋₂₄, C_{ei}, T_{max}, CL, V_z, and apparent terminal t_{1/2}) by population, and the following (non model-based) descriptive statistics will be provided: N (number of subjects with non-missing data), arithmetic mean, standard deviation, arithmetic percent CV (calculated as 100 x standard deviation/arithmetic mean), median, minimum, maximum, geometric mean, and geometric percent CV (calculated as 100 x sqrt(exp(s₂) - 1), where s₂ is the observed variance on the natural log-scale).

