8.1.2.2 Secondary PK Analysis

8.1.2.2.1 Objective 1

Separately for each urine pharmacokinetic parameter, individual values of fe and CL_r will be natural log-transformed and evaluated with a linear fixed effects model, which is described in the primary analysis. Ninety-five percent (95%) confidence intervals for the least squares means for each population will be constructed. To compare subjects with HI in each of the hepatic insufficient categories (moderate HI and severe HI) to matching subjects with normal hepatic function, a two sided 90% confidence interval for the true difference in means (HI – normal hepatic function) will be calculated for each urine PK parameters (fe and CL_r).

Individual values will be listed for each urine PK parameter (fe and CL_r) by population, and non model-based descriptive statistics will be provided

8.1.2.2.2 Objective 2

The safety and tolerability of MK-3866 will be evaluated by clinical assessment of adverse experiences and other safety measurements. Summary statistics for the laboratory safety tests, ECGs, and/or vital signs may also be provided, as deemed clinically appropriate.

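### Does leaving the levels of the population factor unlisted put the control group for each hepatic impairment ratio in doubt?

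*Combined protocol and SAP*

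**What the plan says.** Section 8.1.2.1 takes each plasma PK parameter in turn. The log values are "evaluated with a linear fixed effects model containing a categorical effect for populations", with a grouped residual structure in SAS PROC MIXED "to estimate separate variances for each population" and Kenward-Roger degrees of freedom. Each HI category is then compared "to matching subjects with normal hepatic function" by a two-sided 90% interval, and "For each of the HI populations, these confidence limits will be exponentiated" to give the interval for the ratio. The section also promises "Figures showing individual pharmacokinetic values with GMs (95% confidence intervals) by population", plus descriptive statistics by population. Section 8.1.2.2.1 carries the model over to the urine parameters, which are "evaluated with a linear fixed effects model, which is described in the primary analysis".

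Section 2.1 sets the control rule. Six healthy subjects are first enrolled to match the mean BMI (±10%) and mean age (±15 years) of the HI panel that fills first. If any of them fails to match the second panel, further controls are added until six match it, up to 12 in total. The PK comparisons "will include only control subjects who meet the matching criteria for the respective HI panel". The precision statement in Section 8.1.1 rests on the same basis: "With 6 hepatic insufficient subjects and 6 healthy matched subjects".

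**The concern.** The statistical section names a factor without naming its levels. The obvious coding is moderate, severe and healthy. If Panel C exceeds six, at least one control does not match the second panel, and a single healthy level would then bring that control into a comparison from which Section 2.1 excludes it. Nor does Section 8.1.2.1 say how a control who matches both panels is coded, or which controls form the healthy geometric mean, the figures and the descriptive summaries.

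The stake would be the denominator of the primary ratios. The second panel to fill is the one exposed, and Section 2.1 expects that to be severe HI. The trial is open-label, so a control set left undefined could in principle be chosen with concentrations in view.

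**Working it through.** **Inputs.** Section 8.1.1: healthy between-subject variance of log AUC0-inf 0.0196; doubled to 0.0392 for severe HI; 6 against 6; 90% interval; stated half-width 0.179. Section 2.1: Panel C between 6 and 12, with six controls matching the second panel.

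**The plan's own figure.** SE = sqrt(0.0392/6 + 0.0196/6) = sqrt(0.0098) = 0.0990. With 10 df, t = 1.8125 and the half-width is 0.1794, which reproduces 0.179. Satterthwaite df, as an approximation to Kenward-Roger with separate variances, are 9.0; then t = 1.8331 and the half-width is 0.1815, a factor of 1.199. (The lower-limit divisor 1.163 in Section 8.1.1 does not follow from 0.179, since exp(0.179) = 1.196, but that section's worked interval does. This has no bearing on the present point.)

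**Is the control set defined?** Yes, by arithmetic on age and BMI at screening against a panel mean. For the second panel, the matching controls among the first six must be counted before any are added, because that count fixes how many are added. No concentration enters the rule.

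**Do the matched codings differ?** With one mean and one variance per level, the likelihood separates by level. Each least squares mean is the mean of its own subjects, and each variance is their sample variance. Two pairwise fits, or one fit with shared controls entered in two healthy levels, therefore give the same contrast and SE. Splitting Panel C into first-only, second-only and shared levels can leave one subject in a level, with 0 df and no estimable variance. That coding fails visibly, and the plan does not propose it.

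**How often would it arise?** The documents give no BMI distribution. Assuming a mean of 27–31 and SD of 3–6 in both HI panels, and simulating the BMI rule alone, Panel C exceeds six in 64–79% of trials if controls spread over the ±10% window and in 26–53% if all lie within ±5%. As a hand check, assumed panel means of 29 and 30 give windows of 26.1–31.9 and 27.0–33.0. With controls uniform over the first window, 1 − (4.9/5.8)^6 = 64%. So the situation is not rare.

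**What would the excluded reading do?** If all n controls were pooled, the SD of the chance shift in the second panel's log ratio is sqrt(0.0196 × (1/6 − 1/n)).

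| Panel C size | SD of log shift | As % | Shift if unmatched controls differ in AUC by 10% / 20% (assumed) |
|---|---|---|---|
| 7 | 0.0216 | 2.2% | – |
| 8 | 0.0286 | 2.9% | 1.10^(2/8) = 1.024 / 1.20^(2/8) = 1.047 |
| 12 | 0.0404 | 4.1% | 1.10^(6/12) = 1.049 / 1.20^(6/12) = 1.095 |

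The chance column is sampling difference, not bias: with equal AUC in matched and unmatched controls and 12 pooled, simulated coverage stays at 0.90. It falls to 0.86 and 0.73 if the unmatched controls' AUC is 1.1 or 1.25 times that of the matched ones.

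**Precision.** Keeping to matched controls costs little: severe half-width 0.182 for 6 against 6, compared with 0.169 for 6 against 12. The first panel may gain added controls who also match it. If that panel is moderate HI with variance 0.0196, the half-width moves from 0.1465 with six controls to 0.136 with eight.

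**The case for a change.** The best argument for a change is that intent is not implementation. One healthy least squares mean cannot represent two control sets. The protocol otherwise treats Panel C as a single healthy group, so a programmer working from Section 8.1.2.1 alone might code three levels. Section 2.1 speaks only of PK comparisons, so the published healthy geometric mean might be the denominator of neither ratio. The situation is likely enough to matter, and settling it in writing would take two sentences.

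Part of this stands. The levels are not listed, no other section lists them, and the healthy summaries will need a label saying which controls they contain. But the harmful coding contradicts Section 2.1 and the matching condition in Section 8.1.2.1 itself, so it would be a departure from the plan and not a reading of it. The open-label argument also falls away, because membership follows from screening age and BMI. Showing Panel C as one group in descriptive tables beside matched ratios is acceptable when labelled.

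Section 8.1.2.1 also refers to the model's mean square error, which is not a single quantity when variances are separate. That is a different wording question and does not affect who the controls are.

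**Conclusion.** No change follows. The control set for each ratio is fixed by numeric rules in Section 2.1, and the statistical section respects them through its matching condition. What is missing is the coding. An analyst would supply it by fitting the stated model to each HI panel with its own matched controls, letting shared controls appear in both fits.

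If Section 2.1 is followed, the effect on the matched ratios is nil, and there is nothing to resolve if Panel C stays at six. The shifts of 2.2% to 4.1% by chance, and 2.4% to 9.5% under assumed AUC gaps of 10% and 20%, arise only if the matched-only rule is broken. The conclusion assumes that separate variances are used as stated, so that the matched codings agree, and that reported healthy means are labelled with the controls they include. The trial estimates ratios without a hypothesis test or margin, so no decision threshold depends on this detail.

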8.1.2.2 Secondary PK Analysis

8.1.2.2.1 Objective 1

Separately for each urine pharmacokinetic parameter, individual values of fe and CL_r will be natural log-transformed and evaluated with a linear fixed effects model, which is described in the primary analysis. Ninety-five percent (95%) confidence intervals for the least squares means for each population will be constructed. To compare subjects with HI in each of the hepatic insufficient categories (moderate HI and severe HI) to matching subjects with normal hepatic function, a two sided 90% confidence interval for the true difference in means (HI – normal hepatic function) will be calculated for each urine PK parameters (fe and CL_r).

Individual values will be listed for each urine PK parameter (fe and CL_r) by population, and non model-based descriptive statistics will be provided

8.1.2.2.2 Objective 2

The safety and tolerability of MK-3866 will be evaluated by clinical assessment of adverse experiences and other safety measurements. Summary statistics for the laboratory safety tests, ECGs, and/or vital signs may also be provided, as deemed clinically appropriate.

9.0 LABELING, PACKAGING, STORAGE AND RETURN OF CLINICAL SUPPLIES

9.1 Investigational Product

The investigator shall take responsibility for and shall take all steps to maintain appropriate records and ensure appropriate supply, storage, handling, distribution and usage of

investigational product in accordance with the protocol and any applicable laws and regulations.

Clinical Supplies will be provided by the Sponsor as summarized in Table 8.

Table 8 Product Descriptions

Product Name & Potency	Dosage Form
MK-3866 180 mg	Lyophilized Powder for Injection

MK-3866 clinical supplies will be supplied as a sterile lyophilized powder to be reconstituted and diluted in saline for IV infusion. The lyophilized powder will be reconstituted at the CRU with 12 mL of 0.9% sodium chloride for injection (normal saline) in the original vial to make a stock solution that is further diluted with saline to accommodate the study protocol dose of 150 mg.

9.2 Packaging and Labeling Information

Clinical supplies will be affixed with a clinical label in accordance with regulatory requirements.

9.3 Clinical Supplies Disclosure

This trial is open-label; therefore, the subject, the trial site personnel, the Sponsor and/or designee are not blinded. MK-3866 IV infusion is included in the label text; random code/disclosure envelopes or lists are not provided.

9.4 Storage and Handling Requirements

Clinical supplies must be stored in a secure, limited-access location under the storage conditions specified on the label.

Receipt and dispensing of trial medication must be recorded by an authorized person at the trial site.

Clinical supplies may not be used for any purpose other than that stated in the protocol.

9.5 Discard/Destruction>Returns and Reconciliation

The investigator is responsible for keeping accurate records of the clinical supplies received from the Sponsor or designee, the amount dispensed to and returned by the subjects and the amount remaining at the conclusion of the trial. For all trial sites, the local country Sponsor personnel or designee will provide appropriate documentation that must be completed for drug accountability and return, or local discard and destruction if appropriate. Where local discard and destruction is appropriate, the investigator is responsible for ensuring that a local discard/destruction procedure is documented.

10.0 ADMINISTRATIVE AND REGULATORY DETAILS

10.1 Confidentiality

10.1.1 Confidentiality of Data

By signing this protocol, the investigator affirms to the Sponsor that information furnished to the investigator by the Sponsor will be maintained in confidence, and such information will be divulged to the institutional review board, ethics review committee (IRB/ERC) or similar or expert committee; affiliated institution and employees, only under an appropriate understanding of confidentiality with such board or committee, affiliated institution and employees. Data generated by this trial will be considered confidential by the investigator, except to the extent that it is included in a publication as provided in the Publications section of this protocol.

10.1.2 Confidentiality of Subject Records

By signing this protocol, the investigator agrees that the Sponsor (or Sponsor representative), IRB/ERC, or regulatory authority representatives may consult and/or copy trial documents in order to verify worksheet/case report form data. By signing the consent form, the subject agrees to this process. If trial documents will be photocopied during the process of verifying worksheet/case report form information, the subject will be identified by unique code only; full names/initials will be masked prior to transmission to the Sponsor.

By signing this protocol, the investigator agrees to treat all subject data used and disclosed in connection with this trial in accordance with all applicable privacy laws, rules and regulations.

10.1.3 Confidentiality of Investigator Information

By signing this protocol, the investigator recognizes that certain personal identifying information with respect to the investigator, and all subinvestigators and trial site personnel, may be used and disclosed for trial management purposes, as part of a regulatory submissions, and as required by law. This information may include:

1. name, address, telephone number and e-mail address;
2. hospital or clinic address and telephone number;
3. curriculum vitae or other summary of qualifications and credentials; and
4. other professional documentation.

Consistent with the purposes described above, this information may be transmitted to the Sponsor, and subsidiaries, affiliates and agents of the Sponsor, in your country and other countries, including countries that do not have laws protecting such information. Additionally, the investigator's name and business contact information may be included when reporting certain serious adverse events to regulatory authorities or to other investigators. By signing this protocol, the investigator expressly consents to these uses and disclosures.

If this is a multicenter trial, in order to facilitate contact between investigators, the Sponsor may share an investigator's name and contact information with other participating investigators upon request.

10.1.4 Confidentiality of IRB/IEC Information

The Sponsor is required to record the name and address of each IRB/IEC that reviews and approves this trial. The Sponsor is also required to document that each IRB/IEC meets regulatory and ICH GCP requirements by requesting and maintaining records of the names and qualifications of the IRB/IEC members and to make these records available for regulatory agency review upon request by those agencies.

10.2 Compliance with Financial Disclosure Requirements

Financial Disclosure requirements are outlined in the US Food and Drug Administration Regulations, Financial Disclosure by Clinical Investigators (21 CFR Part 54). It is the Sponsor's responsibility to determine, based on these regulations, whether a request for Financial Disclosure information is required. It is the investigator's/subinvestigator's responsibility to comply with any such request.

The investigator/subinvestigator(s) agree, if requested by the Sponsor in accordance with 21 CFR Part 54, to provide his/her financial interests in and/or arrangements with the Sponsor to allow for the submission of complete and accurate certification and disclosure statements. The investigator/subinvestigator(s) further agree to provide this information on a Certification/Disclosure Form, commonly known as a financial disclosure form, provided by the Sponsor. The investigator/subinvestigator(s) also consent to the transmission of this information to the Sponsor in the United States for these purposes. This may involve the transmission of information to countries that do not have laws protecting personal data.

10.3 Compliance with Law, Audit and Debarment

By signing this protocol, the investigator agrees to conduct the trial in an efficient and diligent manner and in conformance with this protocol; generally accepted standards of Good Clinical Practice (e.g., International Conference on Harmonization of Technical Requirements for Registration of Pharmaceuticals for Human Use Good Clinical Practice: Consolidated Guideline and other generally accepted standards of good clinical practice); and all applicable federal, state and local laws, rules and regulations relating to the conduct of the clinical trial.

The Code of Conduct, a collection of goals and considerations that govern the ethical and scientific conduct of clinical investigations sponsored by Merck, is provided in Section 12.1 - Merck Code of Conduct for Clinical Trials.

The investigator also agrees to allow monitoring, audits, IRB/ERC review and regulatory authority inspection of trial-related documents and procedures and provide for direct access to all trial-related source data and documents.

The investigator agrees not to seek reimbursement from subjects, their insurance providers or from government programs for procedures included as part of the trial reimbursed to the investigator by the Sponsor.

The investigator shall prepare and maintain complete and accurate trial documentation in compliance with Good Clinical Practice standards and applicable federal, state and local laws, rules and regulations; and, for each subject participating in the trial, provide all data, and, upon completion or termination of the clinical trial, submit any other reports to the Sponsor as required by this protocol or as otherwise required pursuant to any agreement with the Sponsor.

Trial documentation will be promptly and fully disclosed to the Sponsor by the investigator upon request and also shall be made available at the trial site upon request for inspection, copying, review and audit at reasonable times by representatives of the Sponsor or any regulatory authorities. The investigator agrees to promptly take any reasonable steps that are requested by the Sponsor as a result of an audit to cure deficiencies in the trial documentation and worksheets/case report forms.

The investigator must maintain copies of all documentation and records relating to the conduct of the trial in compliance with all applicable legal and regulatory requirements. This documentation includes, but is not limited to, the protocol, worksheets/case report forms, advertising for subject participation, adverse event reports, subject source data, correspondence with regulatory authorities and IRBs/ERCs, consent forms, investigator's curricula vitae, monitor visit logs, laboratory reference ranges, laboratory certification or quality control procedures and laboratory director curriculum vitae. By signing this protocol, the investigator agrees that documentation shall be retained until at least 2 years after the last approval of a marketing application in an ICH region or until there are no pending or contemplated marketing applications in an ICH region or until at least 2 years have elapsed since the formal discontinuation of clinical development of the investigational product. Because the clinical development and marketing application process is variable, it is anticipated that the retention period can be up to 15 years or longer after protocol database lock. The Sponsor will determine the minimum retention period and notify the investigator when documents may be destroyed. The Sponsor will determine the minimum retention period and upon request, will provide guidance to the investigator when documents no longer need to be retained. The sponsor also recognizes that documents may need to be retained for a longer period if required by local regulatory requirements. All trial documents shall be made available if required by relevant regulatory authorities. The investigator must consult with and obtain written approval by the Sponsor prior to destroying trial and/or subject files.

ICH Good Clinical Practice guidelines recommend that the investigator inform the subject's primary physician about the subject's participation in the trial if the subject has a primary physician and if the subject agrees to the primary physician being informed.

The investigator will promptly inform the Sponsor of any regulatory authority inspection conducted for this trial.

Persons debarred from conducting or working on clinical trials by any court or regulatory authority will not be allowed to conduct or work on this Sponsor's trials. The investigator will immediately disclose in writing to the Sponsor if any person who is involved in conducting the trial is debarred or if any proceeding for debarment is pending or, to the best of the investigator's knowledge, threatened.

In the event the Sponsor prematurely terminates a particular trial site, the Sponsor will promptly notify that trial site's IRB/IEC.

According to European legislation, a Sponsor must designate an overall coordinating investigator for a multi-center trial (including multinational). When more than one trial site is open in an EU country, Merck, as the Sponsor, will designate, per country, a national principal coordinator (Protocol CI), responsible for coordinating the work of the principal investigators at the different trial sites in that Member State, according to national regulations. For a single-center trial, the Protocol CI is the principal investigator. In addition, the Sponsor must designate a principal or coordinating investigator to review the trial report that summarizes the trial results and confirm that, to the best of his/her knowledge, the report accurately describes the conduct and results of the trial [Clinical Study Report (CSR) CI]. The Sponsor may consider one or more factors in the selection of the individual to serve as the Protocol CI and or CSR CI (e.g., availability of the Protocol/CSR CI during the anticipated review process, thorough understanding of clinical trial methods, appropriate enrollment of subject cohort, timely achievement of trial milestones). The Protocol CI must be a participating trial investigator.

